Sample Tracking, Management and Storage: After sample obtainment, processing and storage, samples will initially be batched sent to the University of Pittsburgh biological sample repository where it will be tracked, managed and stored until the necessary translational or mechanistic measurement are performed. The CCC and DCC have a long track record of coordinating such processes.

Power Analysis: The prospective cohort study will utilize time to 4 hour mortality for its primary outcome to power the study. Based upon the 6 LITES Network sites admission history that will be utilized and their respective volume of hemorrhagic shock patients meeting inclusion and exclusion criteria and a 3.5 year enrollment time period, we plan to initiate sampling on 1,050 patients over the enrollment time period of the study. With an 85% consent rate which is an estimate based upon prior studies of similar nature, we will consent for participation 892 patients for the study. With an estimate baseline rate of 4 hour mortality of 11.1 % derived from the PROPPR study, there will be 90% power to detect a hazard ratio of 1.9.

Calculations are based on the primary aim of the study based on the following assumptions:

- Type I error rate of 0.05
- Two-sided alternative hypothesis

Linking Investigations in Trauma and Emergency Services

Task Order 2: Shock, Whole blood and Assessment of TBI (SWAT)

- 6 sites will be involved, three whole blood and three component sites
- Each site will enroll 175 participants in 3.5 years of enrollment, of which, 85% will be eligible for the study (149)
- The calculations are based on Cox proportional hazard model
- A 4 hour event rate in the control (non-whole blood) group of 0.111

The power calculations for these secondary aims are presented below. When reporting the results of the analyses, caution will need to be taken with respect to the interpretation of the findings since they are secondary in nature.

The secondary outcomes in Aim 1B include binary outcome, continuous outcomes, and time to event outcomes. For the binary outcomes, the odds ratio that can be detected is presented in Table 1. For the continuous outcome, the effect size that can be detected is 0.13. Finally, for the time to event outcomes, the hazard ratio that can be detected over a range of event rates in the control group is also presented in Table 1.

Event Rate	.1	.2	.3	.4	.5	.6
Odds Ratio	1.76	1.56	1.49	1.46	1.46	1.48
Hazard Rate	2.69	1.70	.37	.30	.27	.30

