Hypothesis#1A: For the primary outcome, the time to death will be generated for each participant. Kaplan-Meier curves will be generated for each treatment group and a log-rank test will be used to compare the distribution of the cumulative proportion. A hierarchical Cox-proportional hazards regression model will be used to control for the within-institution clustering. The hierarchical Cox-proportional hazards regression model will then be used to assess the independent impact of whole blood on time to death after controlling for the clustering effect and potential confounding effects of baseline characteristics. The model will include main effects for whole blood usage and a propensity score for receiving whole blood. The propensity score for the use of whole blood will be generated using a boosted logistic regression model. The dependent variable in the model will be the use of whole blood and the independent variables will be the baseline characteristics of the population. The Cox-proportional hazards model will be used to estimate the cumulative probability of death 4 hours.

Hypothesis#1B: The analytic approach for the secondary outcomes included in Hypothesis#1B will vary based on the type of outcome. For binary outcomes (e.g., 12 hour and 24 hour mortality, death from exsanguination, incidence of MOF, nosocomial infection), the same analytic approach that was carried out for Hypothesis 1a will be implemented.

For continuous outcomes (e.g., transfusion ratios, blood transfusion requirements) a two-sided t-test for correlated means will be used to compare the means between those receiving and not receiving whole blood. A hierarchical analysis of variance model will be used to control for the within-institution clustering. The model will be used to assess the independent impact of whole blood after controlling for the clustering effect and the potential confounding. The model will include main effects for whole blood usage and propensity for receiving whole blood.

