Interim Analysis: There will be two aspects of the interim analysis. First, for efficacy, the Lan and Demets approach will be utilized to conduct the interim efficacy analysis. This approach is preferable over other approaches because it is flexible to the number of interim analyses conducted during the course of the study. The Lan and DeMets approach requires the use of a spending function to allocate the type I error to the interim analysis. The O'Brien and Fleming spending function which minimizes the type I error allocated to the interim analysis, saving the vast majority for the primary analyses will be used. For the proposed interim analysis, assuming that 50% of the study will be completed, it is estimated that the type I error allocated to the interim analysis will be 0.005, leaving 0.048 of the type I error for the primary outcome analysis.

Linking Investigations in Trauma and Emergency Services

Task Order 2: Shock, Whole blood and Assessment of TBI (SWAT)

Time Line: The study will occur over a 4 year period with a 6 month start up period, an interim analysis at 2 years and a 3.5 year enrollment period.

Linking Investigations in Trauma and Emergency Services

Task Order 2: Shock, Whole blood and Assessment of TBI (SWAT)

BIBLIOGRAPHY

3. Hoyt DB. A clinical review of bleeding dilemmas in trauma. *Semin Hematol*. 2004;41(1 Suppl 1):40-43.

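### The plan gives no few-site method for the whole-blood test: with six sites split by transfusion practice, the usual test in the hierarchical Cox model would exceed its 5% error rate if sites differ appreciably

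*Combined protocol and SAP*

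**What the plan says.** In the combined protocol and SAP, the Study Setting, Whole Blood Transfusion Sites and Component Transfusion Sites paragraphs choose centres by their existing transfusion practice. The Power Analysis assumptions read "6 sites will be involved, three whole blood and three component sites", with 175 patients enrolled per site and 149 (85%) analysed.

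For the primary outcome, Analyses, Hypothesis#1A, says: "A hierarchical Cox-proportional hazards regression model will be used to control for the within-institution clustering". The model carries a term for whole-blood use and a propensity score built from baseline characteristics. Nothing is said about how the whole-blood coefficient is tested, how the site variance is estimated, or which reference distribution applies.

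The error rate is given as "Type I error rate of 0.05" with a "Two-sided alternative hypothesis". The Interim Analysis section spends 0.005 at the interim look, "leaving 0.048 of the type I error for the primary outcome analysis". The power claim is "there will be 90% power to detect a hazard ratio of 1.9". No between-site SD or intraclass correlation appears, and no expected share of patients at whole-blood sites who will receive whole blood.

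**The concern.** When exposure follows site, more patients per site do not supply more information on how sites differ for other reasons. With three sites in each group, about 4 degrees of freedom (6 - 2) describe that variation. Standard output from a hierarchical Cox model estimates the site variance from six sites, often close to zero, and then treats it as known by comparing the coefficient over its standard error with a normal distribution. The p-value is then too small and the interval too narrow.

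The propensity score does not cure this, because adjusting for patients' baseline characteristics adds no sites. The plan itself expects sites to differ: it anticipates different massive transfusion protocols and different whole-blood products.

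This is the primary hypothesis, and the study is to feed clinical practice guidelines. A difference between a few hospitals could be reported as a whole-blood effect more often than the stated error rate allows. The point concerns the validity of the planned test; it is separate from whether the sample size allowed for clustering.

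**Working it through.** **1. The plan's power figure.** Inputs from Power Analysis: 892 patients, 4-hour rate 0.111, HR 1.9, two-sided 0.05, equal groups. Schoenfeld's formula is power = Φ(√events / 2 × ln HR − 1.96).
- Events: 892 × 0.111 = 99.
- Power: Φ(9.95 / 2 × 0.642 − 1.96) = Φ(1.23) = 89.1%.

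This matches the stated 90%, but only with 0.111 as the rate over both groups and no term for site variation. The assumptions label the rate differently: "A 4 hour event rate in the control (non-whole blood) group of 0.111". With 0.111 in controls only and HR 1/1.9, the whole-blood rate is 1 − 0.889^(1/1.9) = 0.060. Events are then 446 × (0.111 + 0.060) = 76 and power is 80%.

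**2. Size of the site component (hand check).** At 149 × 0.111 = 16.5 deaths per site, the within-site variance of a log hazard is about 1/16.5. A site SD of σ therefore multiplies the variance of the contrast by about 1 + 16.5σ²: 1.66 at σ = 0.2 and 2.49 at σ = 0.3. A Cox model ignoring site would reject 2Φ(−1.96/√1.66) = 13% and 2Φ(−1.96/√2.49) = 21% of true nulls. Simulation gave 12.4% and 22.1%. The question is how much of this excess the hierarchical model removes.

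**3. Type I error of the hierarchical Cox model.** Simulation: six sites of 149, split 3:3, everyone at whole-blood sites exposed, log-normal site frailty, 11.1% 4-hour mortality, censoring at 4 hours, no whole-blood effect. The fit is a shared-frailty Cox model with 4,000 studies per row (Monte Carlo SE about 0.3-0.6 points). Site SD is an assumption; the second column shows what it implies.

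| Site SD | 4-h mortality, 95% of sites | ML Wald | REML Wald | Likelihood ratio | REML, t on 4 df |
|---|---|---|---|---|---|
| 0 | 11.1% | 4.3% | 3.8% | 3.1% | 0.3% |
| 0.1 | 9.2-13.3% | 5.6% | 4.8% | 4.1% | 0.6% |
| 0.2 | 7.6-16.0% | 8.3% | 7.1% | 6.0% | 1.4% |
| 0.3 | 6.3-19.1% | 11.4% | 9.5% | 7.9% | 2.4% |
| 0.4 | 5.2-22.7% | 13.2% | 10.5% | 8.8% | 3.5% |
| 0.5 | 4.3-26.9% | 14.6% | 11.1% | 9.3% | 3.6% |

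At SD 1.0, ML Wald gives 14.4% and REML Wald 11.1%, so the inflation levels off. A 2:4 split (the plan elsewhere expects 33% of patients from whole-blood sites) or 175-198 patients per site gives similar ML values: 8.6-9.4% at SD 0.2 and 11.6-12.2% at 0.3.

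**4. Analytic ceiling.** When site variance dominates, the Wald ratio behaves like a scaled t on 4 df.
- REML: P(|t₄| > 1.96) = 12.2%.
- ML in a Cox model (variance divisor 5): P(|t₄| > 1.96√(4/5) = 1.75) = 15.4%.
- ML with divisor 6: P(|t₄| > 1.96√(4/6) = 1.60) = 18.5%.

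**5. Partial receipt at whole-blood sites** (share assumed; same simulation, except 2,000 studies at 50%).

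| Receipt | ML Wald, SD 0.2 / 0.3 / 0.5 | REML Wald, SD 0.2 / 0.3 / 0.5 |
|---|---|---|
| 90% | 7.6 / 10.2 / 10.4% | 6.8 / 8.9 / 9.1% |
| 80% | 6.8 / 8.4 / 8.1% | 6.5 / 7.7 / 7.5% |
| 50% | not run / 5.9 / 5.2% | not run |

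A separate random-intercept simulation gave 8-12% at 80-90% receipt. For SD 0.2-0.3, about 7-11% is a fair summary.

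**6. A site-level test.** Compare three with three site complementary log-log rates against t on 4 df (critical value 2.78). Under the null it rejects 4.5-5% at SD 0-0.4. For power at HR 1/1.9, each site's variance is p / [149(1 − p)(ln(1 − p))²], which is 0.0605 at p = 0.111 and 0.1118 at p = 0.060. SE = √[(0.0605 + 0.1118 + 2σ²)/3] and the non-centrality is 0.642/SE.
- σ = 0: SE 0.240, non-centrality 2.68, power 53%.
- σ = 0.2: SE 0.290, non-centrality 2.21, power 39%.
- σ = 0.4: SE 0.405, non-centrality 1.58, power 23%.

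Simulation (20,000 studies per SD) gave 52%, 49%, 39%, 29% and 23% at SD 0, 0.1, 0.2, 0.3 and 0.4.

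**7. Interim look.** A two-sided 0.005 corresponds to z = 2.81. In the REML limiting case of step 4, P(|t₄| > 2.81) = 4.8%.

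**The case against.** The strongest reply is that the plan does not commit to a Wald test, a normal reference or maximum likelihood, so it cannot be charged with a known error rate. That is correct as far as it goes: the defect is an unspecified method, and the rates above describe what default output from the named model would give. It still matters, because someone following the text as written would most naturally report that output. The likelihood-ratio test is closer to nominal (6.0% and 7.9% at SD 0.2 and 0.3) but also exceeds it.

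Second, exposure is defined by the patient's use of whole blood, and sites may be added as practice changes. Within-site variation in receipt and more sites both shrink the problem. This stands, and it is why no single rate can be quoted.

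Third, the site SD is assumed, the residual SD after propensity adjustment could be lower, and that adjustment was not simulated. This also stands: at SD 0-0.1 there is essentially nothing to correct.

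A reader might infer a false-positive rate near 20%, or two to four times nominal. The evidence does not support this for the named model. The fitted frailty Cox levels off at about 14-15% (ML) or 11% (REML), and even the extreme ML limit is 18.5%. Rates near 20% arise with a site-robust sandwich standard error (18-20% for a 3:3 split at SD 0.2-0.5) or with no site term, neither of which is what the plan describes.

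**Conclusion.** The concern holds in conditional form. With whole blood set largely by site and six sites, the usual normal-reference Wald test would reject a true null about 7-12% of the time at site SD 0.2-0.3 and up to about 15% at larger SDs, against a stated 5% (0.048 at the final analysis, which makes little difference). Full receipt at whole-blood sites underlies those figures. At 80-90% receipt the rate is about 7-11% for SD 0.2-0.3, and at 50% it is near 5-6%. The documents fix neither quantity, so they establish that error control is not secured, but not by how much it fails.

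The 90% power statement reproduces only if sites do not differ. It does not describe a test that holds its level with six sites.

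**What to change.** In Analyses, Hypothesis#1A, state that the whole-blood p-value and confidence interval use a small-number-of-sites method, chosen by a rule fixed in advance:
- If receipt is essentially all-or-none by site, use a site-level adjusted comparison with a t reference on (sites − 2) df, which holds about 5%.
- If receipt varies within sites, use the REML frailty model with small-sample df, or a parametric-bootstrap null distribution. The bootstrap was not simulated here; its calibration should be checked at the actual site sizes and receipt pattern.

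The two options are not interchangeable. Applying t on (sites − 2) df mechanically to the hierarchical model over-corrects (1.4% rejection at SD 0.2, 2.4% at 0.3), and a two-group site-level test discards within-site information where there is any.

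Report the uncorrected model result alongside. Use the same method at the interim look, and update it if sites are added. In Power Analysis, restate what the study can conclude: for HR 1/1.9 the site-level test has about 50% power at SD 0 and roughly 20-40% at SD 0.2-0.4.

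The cost is SAP wording and a small extra analysis. The downside is real: wider intervals (critical value 2.78 rather than 1.96 for the site-level test at six sites) and a clearly less favourable power statement.

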Hypothesis #1B: *Whole blood resuscitation will be associated with a lower incidence of 12 hour and 24 hour mortality, a lower incidence of death from exsanguination, incidence of MOF, nosocomial infection, improved transfusion ratios, lower overall blood transfusion requirements and shorter time to hemostasis as compared to those resuscitated with component therapy.*

Hypothesis #1C: *Whole blood resuscitation will be associated with an improved Glasgow Outcome Score-Extended at 6 months post injury as compared to those resuscitated with component therapy in patients with traumatic brain injury.*

Hypothesis #2A: *A nadir prehospital and acute phase resuscitation systolic blood pressure greater than or equal to 120 mmHg will be associated with improved traumatic brain injury outcomes at discharge and at 6 months.*

Linking Investigations in Trauma and Emergency Services

Task Order 2: Shock, Whole blood and Assessment of TBI (SWAT)

Hypothesis #2B: *The magnitude of the dose depth curve of systolic blood pressure during the prehospital and acute phase resuscitation will be associated with neurological outcome differences at discharge and at 6 months following traumatic brain injury.*

Research Design and Methods

Study Design: The LITES Network will perform a multicenter, prospective, observational cohort study over a 4 year period to determine the impact of whole blood resuscitation in trauma patients with hemorrhagic shock at risk of large volume resuscitation with and without TBI. Early whole blood resuscitation will be compared to standard component resuscitation. The study will also further characterize blood pressure and resuscitation endpoints in poly-trauma patients with traumatic brain injury. Six trauma sites with appropriate characteristics will be selected from network sites across the country. (Figure 2)

Figure 2

Study Setting: The study will be performed utilizing busy level I trauma centers from within the LITES Network located across the country, at sites where either whole blood has currently been incorporated into standard of care or where component blood transfusion is being utilized for patients in hemorrhagic shock at risk for large volume resuscitation. Due to the paucity of trauma centers who are currently utilizing whole blood for trauma patients as standard of care, the potential to incorporate additional sites may be required over time.

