Study Population: The study will focus on patients who suffer blunt or penetrating injury, transported to a Task Order 002 participating LITES trauma center with evidence of hemorrhagic shock at risk of large volume resuscitation.

Inclusion Criteria: Patients with blunt or penetrating injury who meet the following criteria: 1, 2, and 3

- 1) Has 2 or more of any of the following:
 - a. Hypotension (systolic blood pressure \leq 90 mmHg) in the prehospital setting or within 60 minutes of hospital arrival,
 - b. Penetrating mechanism,
 - c. FAST abdominal ultrasound is positive or equivocal or deferred by clinical team due to emergent visit to Interventional Radiology or a need for emergent laparotomy, thoracotomy, or vascular exploration.

Linking Investigations in Trauma and Emergency Services

Task Order 2: Shock, Whole blood and Assessment of TBI (SWAT)

- d. Heart Rate \geq 120 in the prehospital setting or within 60 minutes of hospital arrival.

AND

- 2) Taken to the Operating Room (laparotomy, thoracotomy or vascular exploration) or Interventional Radiology within 60 minutes of arrival.

AND

- 3) Blood/blood component transfusion in prehospital setting, ED or OR within 60 minutes of arrival.

Exclusion Criteria:

- 1) Age < 15
- 2) CPR > 5 consecutive minutes without ROSC
- 3) Penetrating brain injury with brain matter exposed
- 4) ED death
- 5) Known pregnancy
- 6) Known Prisoners

Inclusion and exclusion criteria will be assessed based on available information at the time of enrollment. Although all reasonable efforts will be made by the prehospital crew to either directly witness or obtain documentation of qualifying vitals, due to the nature of the emergency pre-hospital setting, there may be occasions where the prehospital medical crew must rely on verbal report of inclusion criteria, including qualifying vitals, from the referring hospital or EMS agency. In these instances, if, after subsequent review of outside hospital and/or EMS agency documentation, it is determined that the subject did not meet inclusion criteria and/or met exclusion criteria, the subject will remain enrolled in the study based on the information available at the time the subject was enrolled in the study.

Recruitment and Consent

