Samples are required in the first 36 hours in order to determine the underlying mechanisms of whole blood benefit, which is one of the main objectives of the study. Sampling needs to occur approximately at the time of whole blood transfusion and soon after. Whole blood and component arm transfusion, in these severely injured trauma patients, will for the majority of patients occur within the first 4 hours of admission. Sampling at the proposed time points in the first 36-hours are essential and have to occur in relationship to this early whole blood and component transfusion window. Sampling beyond these early time points will not allow the main objectives of the study to be accomplished.

Whenever appropriate, the subjects will be provided with additional pertinent information after participation. [45 CFR 46.116 (d)(4)].

Subjects whose medical conditions improve to the point of being able to make their own medical decisions will sign a HIPAA-compliant consent to continue further study-related procedures. Subjects who remain critically ill, receiving continuous or intermittent sedatives, who are

Linking Investigations in Trauma and Emergency Services

Task Order 2: Shock, Whole blood and Assessment of TBI (SWAT)

obtunded/disoriented from illness or injury, or are unable to dictate their own care will have proxy consent obtained in compliance with local regulations.

A Waiver of HIPAA Authorization is also requested and justified, to be used in conjunction with the Waiver of Consent [B], for the extraction of research data from the medical record.

To ensure that this research use of the PHI involves no greater than minimal risk to privacy, describe your plan to protect patient-subject identifiers from improper use or disclosure. [45 CFR 164.512 (i)(2)(ii)(A)(1)]

All electronic data will be stored on a secure password protected server. Each subject will be given a unique study identifier, which will be used for all patient samples and all clinical data sheets. The key to identify subjects with their unique study number will be kept on a secure drive and only accessed by the PI, co-investigators or their designees according to the University of Pittsburgh and UPMC policies.

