- For Aim 1C, a nonparametric analysis of variance will be used to compare the distribution of the GOS-E between the two groups. An effect size of 0.17 could be detected.
- For aim 2A, a nonparametric analysis of variance will be used to compare the distribution of the GOS-E between the two groups. An effect size of 0.28 could be detected.
- For aim 2B, a nonparametric correlation coefficient will be used to assess the association between GOS-E and the area under the systolic blood pressure curve. For each, a 95% confidence interval with a width of 0.19 can be estimated.
- For all secondary analyses, the type I error rate was set to 0.05, with a two-sided alternative hypothesis, and 90% power. For the Aim 1, the sample size will be 1,190. For Aim 2, the sample size will be limited to those with a traumatic brain injury. For the purposes of this study, this is expected to be 35% or a total of 417 participants.

Analyses

AIM#1: The analysis will begin by describing the baseline demographic and clinical characteristics of the overall population and then stratified by whole blood usage. The characteristics will be

Linking Investigations in Trauma and Emergency Services

Task Order 2: Shock, Whole blood and Assessment of TBI (SWAT)

compared among those who receive and who do not receive whole blood. For discrete variables, proportions will be generated and a chi-square test will be used to test for differences between the proportions. For continuous characteristics, means (medians) and standard deviations (interquartile ranges) will be calculated and t-tests (Wilcoxon) will be used to compare the means (distributions) among those who receive and do not receive whole blood.

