Finally, for time to event analyses (e.g., time to hemostasis), a bivariate hierarchical Cox proportional hazards regression model will be generated to compare the time to event between those receiving and those not receiving whole blood. Again, the hierarchical model will be used to control for within-institution clustering. In a second step, to determine the independent effect of whole blood after controlling for potential confounding effects, the propensity score will be added to the model.

Hypothesis#1C: A two-sided z-test for correlated proportions will be used to compare the distribution of GOS-E proportions between those receiving and not receiving whole blood. This

Linking Investigations in Trauma and Emergency Services

Task Order 2: Shock, Whole blood and Assessment of TBI (SWAT)

test will be used to control for the within-institution clustering. A hierarchical polytomous logistics regression model will then be used to assess the independent impact of whole blood after controlling for the clustering effect and the potential confounding effects of baseline characteristics. The model will include main effects for whole blood usage and propensity for receiving whole blood.

AIM#2: The analyses for the second aim will be restricted to the subset of participants who will be characterized as having a traumatic brain injury.

Hypothesis#2A: The analysis will begin by comparing the baseline characteristics of those with a prehospital and acute phase resuscitation systolic blood pressure greater than or equal to 120 mmHg to those who do not. For discrete variables, proportions will be generated and a chi-squared test will be used to test for differences between the proportions. For continuous characteristics, means (medians) and standard deviations (interquartile ranges) will be calculated and t-test (Wilcoxon) test will be used to compare the means (distributions) among those who receive and do not receive whole blood.

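### Aim 1 groups patients by receipt of whole blood with no exposure window or time zero, so the primary hazard ratio is biased toward whole blood whenever components are given first at a whole blood site

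*Combined protocol and SAP*

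**What the plan says.** The Study Design section sets out the contrast: "Early whole blood resuscitation will be compared to standard component resuscitation". Neither that section nor any other says how soon, or in what amount, WB must be given to count as early.

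The Analyses section works from receipt in the individual patient:

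- AIM#1: characteristics are "compared among those who receive and who do not receive whole blood".
- Hypothesis#1A, primary model: "The model will include main effects for whole blood usage and a propensity score for receiving whole blood".
- Hypothesis#1A, propensity model: "The dependent variable in the model will be the use of whole blood". Its predictors are baseline characteristics.
- Hypothesis#1B, time-to-event outcomes: the contrast is "those receiving and those not receiving whole blood". Hypothesis#1C uses the same grouping.

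None of these gives a window, a landmark, a time-dependent term or delayed entry, and Hypothesis#1A does not say when the clock starts. A clock of 4 hours from arrival is implied elsewhere (Time to Hemostasis; Death from Exsanguination/Hemorrhage; Screening/Outcome Data and Sample Collection) but is not tied to the Cox model.

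Inclusion criterion 3 asks for "Blood/blood component transfusion in prehospital setting, ED or OR within 60 minutes of arrival". It is not specific to WB. The Power Analysis assumes three WB and three component sites, but the planned comparison is not made by site type.

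**The concern.** Exposure is settled during the same 4 hours in which the primary outcome is counted. Take a patient at a WB site who is given components first. If the patient dies before WB arrives, the death goes to the comparator. If the patient survives to receive WB, the whole record, including the interval in which death would have prevented exposure, goes to the WB group. Deaths are removed from one side and added to the other even if WB does nothing.

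The propensity score is built from baseline characteristics. It balances who tends to get WB; it does not repair a grouping that depends on survival after baseline.

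At stake is the primary hazard ratio of a cohort that is to inform WB Clinical Practice Guidelines (Executive Summary, AIM#1). With the definition open, two analysts could also get different primary results from the same data.

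**Working it through.** **The plan's own figure.** The Power Analysis gives 90% power for a hazard ratio (HR) of 1.9 with 892 patients and a 4-hour event rate of 0.111. Events: 892 × 0.111 = 99. With 1:1 groups, power = Φ(√(99/4) × ln 1.9 − 1.96) = Φ(1.23) = 0.89. This reproduces the figure and is not in dispute. In the direction of benefit the target HR is 1/1.9 = 0.53.

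**Hand calculation of the mechanism (no true effect).** The event rate is from the plan; the timing is assumed.

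1. Constant hazard: −ln(1 − 0.111)/4 = 0.0294 per hour.
2. Take 1,000 patients, 500 per site type, with 55.5 deaths by 4 hours in each. At WB sites 250 get WB first, and 250 get it at 60 minutes if alive.
3. Deaths before WB: 250 × (1 − e^−0.0294) = 7.2.
4. Grouped by receipt, WB has 55.5 − 7.2 = 48.3 deaths in 492.8 patients (9.8%), and the comparator 55.5 + 7.2 = 62.7 deaths in 507.2 (12.4%).
5. Person-hours: 500 × 0.111/0.0294 = 1,887 per site type. About 7.2 × 0.5 = 3.6 move across.
6. Rate ratio: (48.3/1,883)/(62.7/1,891) = 0.77, where the truth is 1.

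**Simulation with the entry rules.** All timings are assumptions, because the documents give none:

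- OR/IR entry uniform over 10-60 minutes after arrival.
- First product prehospital in 20%, otherwise uniform over 0-60 minutes.
- Criterion 1 met at arrival in 80%, otherwise within 60 minutes.
- All patients alive when the last criterion is met; 11.1% dead by 4 hours; exponential deaths; half the patients at WB sites.
- Component-first patients at WB sites get WB after an exponential delay, if alive.

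Unadjusted HR, true HR 1:

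| WB first at WB sites | median delay 15 min | 30 min | 60 min |
|---|---|---|---|
| 90% | 0.98 | 0.97 | 0.96 |
| 75% | 0.97 | 0.92 | 0.89 |
| 50% | 0.94 | 0.86 | 0.78 |

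A separate simulation gave 0.94-0.99, 0.89-0.96 and 0.78-0.94 for the three rows, which agrees within about 0.02. WB always first gave 0.99-1.00. Classification at time zero gave 0.99-1.01.

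**Does the planned adjustment help?** A site random effect with 892 patients did not reduce the bias (0.95-0.99, 0.87-0.97, 0.65-0.93). In a variant where later WB also depends on severity, a site effect plus a propensity score capturing severity fully still left 0.97-0.99, 0.90-0.98 and 0.78-0.95.

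**A separate mechanism.** Suppose 30% of patients have 4 times the hazard, and lower-risk component-first patients never get WB. With WB first in 50%, the unadjusted HR was 1.38 (15 min) and 1.18 (60 min). Within the higher-risk stratum it was 0.94 and 0.78; within the lower-risk stratum 1.01 and 1.02. The excess above 1 is therefore confounding by severity, and the survival-dependent part still favours WB.

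**The case against.** The strongest reply is that WB will be the first product at WB sites. Those sites are chosen for urgent-release programmes, WB is described as standard of care, and the Preliminary Data describe release in the emergency department without typing or cross-matching. If so, the bias is close to nil. This stands as a limit on size. But the site criteria also admit centres still implementing a programme, no WB-first share is given, and the analysis would apply the same rule whatever that share is.

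Nor do the documents show that WB usually follows components. The waiver text that transfusion "will for the majority of patients occur within the first 4 hours of admission" covers both arms and justifies sampling times, and Table 1 marks the same columns for both products. They allow a late first WB unit; they do not establish one.

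Two stronger readings are tempting and are not supported. A reader might infer that the plan defines exposure as WB at any time. It does not: it is silent, and the design says *early*. A reader might also infer that dependence on survival can bias the result in either direction. In the calculations it pushes only toward WB; estimates above 1 came from severity-driven receipt and vanished within severity strata.

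**Conclusion.** The point holds and should be fixed. Followed as written, the Aim 1 grouping biases the primary HR toward WB whenever some WB-site patients receive components first and some of them die before WB. Later WB given for continuing bleeding is confounding by severity, a different problem that can push the other way, so the net direction is not known.

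The size is uncertain. Against the target HR of 0.53, a spurious 0.94 is ln 0.94/ln 0.53 = 10% of the log effect and a spurious 0.78 is 39%. These figures rest wholly on the assumed WB-first share and delay. Other assumptions move them: deaths concentrated earlier gave values down to 0.73 at a 50% share, and 33% of patients at WB sites with exponential deaths gave a smaller bias (0.82 instead of 0.78 at 50% and 60 minutes). Confidence is high that the definition is open to this bias, and low on how large it will be.

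**What to change.** In Hypothesis#1A:

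- State that death is counted to 4 hours from arrival.
- Set time zero from recorded times, for example the later of OR/IR entry and first blood product, not before arrival. Start follow-up there by delayed entry.
- Classify exposure by WB received by time zero, and use the same definition in the propensity model and in Hypotheses 1B and 1C.
- Add two sensitivity analyses: WB as a time-dependent covariate (0 until the first unit, 1 after), and WB site versus component site.
- Report how many WB-site patients first received WB after time zero, or never.

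This costs plan wording and one derived variable. Arrival and transfusion times are already listed under Data Collection, and OR/IR entry time is needed to verify criterion 2. The moment criterion 1 was met is best left out of time zero, because FAST timing is not among the listed items.

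Downsides:

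- Later WB recipients count as component. In the simulation, whose time zero also included criterion 1, these were 6-8%, 15-21% and 29-42% of WB-site patients at the three WB-first shares. A true HR of 0.53 was then estimated as about 0.54, 0.56 and 0.58-0.59.
- Confounding by severity can remain: up to 1.18 unadjusted at time zero in the severity setting, and 1.02-1.40 for the time-dependent term.
- The site comparison avoids individual receipt (0.99-1.02 in that setting) but rests on six sites and carries any other differences between them.
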